5.1.1 Randomisation and Blinding aspects

Following written consent patients will be allocated at random to the one of two treatment arms. Participants are stratified by ulcer size (PUSH score) at baseline, ie week 0.

A non-restricted randomised sequence will generated for each of the two groups using a freeware randomisation programme, see https://www.sealedenvelope.com/. The randomisation will be stratified by ulcer size, with one group being those with a PUSH score of up to and including 8, or a PUSH score of 9 or higher

Each next randomisation allocation will be obtained from the sealedenvelope.com account for this CUPRA trial.

As the study involves different looking dressings, it is not possible to achieve blinding for the participants. However, statistical analysis is carried out blinded to group allocation, by persons who have not had contact with study participants.

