Prospective, randomised controlled trial assessing MedCu copper dressing for lower limb ulcer management

(CUPRA trial, Copper dressings for Ulcers; Prospective Randomised Appraisal)

Version 1.0, dd 18 October 2024

Chief Investigator's Statement of Ownership and Content.

I, [name], confirm that this protocol is my work and is owned by me. The protocol conforms with standards outlined in the Declaration of Helsinki 1964.

Name (PRINT):____[name]______

Signature:_______

Date: _________

RESEARCH PROTOCOL SUMMARY

| TITLE: | Prospective, randomised controlled trial assessing MedCu copper dressing for lower limb management | | | |
|----------------------|---|--|--|--|
| | (CUPRA trial, Copper dressings for lower limb Ulcers; Prospective Randomised Appraisal) | | | |
| Short title: | CUPRA trial | | | |
| IRAS ethics number | 350241 | | | |
| ISRCTN trial number | To be confirmed | | | |
| Device description | CE-marked wound dressing: MedCu (by MedCu Technologies) dressings are impregnated with copper oxide microparticles. MedCu dressings are single-use wound dressing with an internal absorbent layer and one or two external non-woven, non-adherent layers. | | | |
| Study design | Prospective, randomised controlled trial | | | |
| Primary objective | To determine the relative efficacy and safety of MedCu copper-impregnated dressing versus standard of care for the management of lower limb ulcers, measured through wound status (healed vs non-healed) at 12 weeks post-baseline. | | | |
| Secondary objectives | To determine the wider efficacy and safety of MedCu copper- impregnated dressing for the management of lower limb ulcers at 4, 8 and 12 weeks post-baseline - Any adverse events related to the use of allocated dressings, and rates of (patient-requested) discontinuation of dressing Wound status (healed vs non-healed) - Quality of Life (EQ-5D-5L) - Lower limb symptoms (VEINES Sym) - Types of dressings applied in standard care arm | | | |
| Patient population | First known randomised controlled trial of MedCu dressing. Therefore pragmatic approach to allow inclusion of wider cohort of patients. Patients with lower limb ulcer of any underlying aetiology are considered for inclusion. Index wound size should be minimum of 1cm² and can be maximum of 30cm² (only one index wound per patient to be included in study). Stratification for wound size at randomisation stage. | | | |

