| | Participants must not be palliative and have the mental and physical capacity to provide informed written consent and complete patient reported outcome measures. Participants are recruited from the local hospital / community clinics. |
|--------------------|---|
| Sample size | The primary outcome, wound status (healed vs non-healed) is used for sample size calculation. Treatment will be random and 1:1 allocation: n = 33 standard of care and n = 33 MedCu copper dressing cases, giving a combined total of n = 66 participants. |
| | The sample size calculation is based on 2x2 Chi-squared test (80% power and 5% alpha). The hypothesis is a minimum 20% (effect size 0.40) difference in wound healed at week 12, with then allocation for 30% withdrawal/dropout rate added. |
| | Option to expand sample size, subject to review of safety data, after initial sample size has been reached. This then allows wound healing comparison for purer sample of 'leg ulcers' and 'foot ulcers' separately from each other. For each of these subsamples, 66 participants are to be recruited. |
| Sponsor | North Cumbria Integrated Care NHS Foundation Trust |
| Funder | Creed Health [name] [contact] Email: [contact] E: [contact] W: https://www.creedhealth.co.uk/ |
| Chief Investigator | [name], vascular specialist nurse, Vascular Surgery Dept, North Cumbria University Hospitals NHS Trust, Cumberland Infirmary, [name] [contact] |
| Co-investigators | [name] PhD, Research Project Lead, [contact]; Cumbria Partnership NHS Foundation Trust R&D Department, Cumberland Infirmary, [name] [contact] |
| | [name], Head of Podiatry, North Cumbria Integrated Care NHS Foundation Trust, Cumberland Infirmary, [name], [contact] |

| Organisations where research will take place | North Cumbria Integrated Care NHS Foundation Trust Cumberland Infirmary, [name] | | | |
|--|--|--|--|--|
| | Optional: up to 2 other NHS Trusts, exact sites to be determined (once trial has been listed on National Institute for Health Research National Portfolio) – amendment to be | | | |
| | submitted to HRA once additional site identified. | | | |
| Planned timeline | First patient, first visit: 1Mar2025, | | | |
| | Last patient, first visit: 31Apr2026 | | | |
| | Last patient, last visit: 30Jul2026 | | | |
| | Trial end date: 30Sep2026 | | | |

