5. SUBJECTS

5.1 Anticipated number of research subjects

Below a summary is given for the sample size needed. The primary outcome, wound status (healed vs non-healed) is used for sample size calculation for both randomisation groups.

The sample size calculation has been performed using GPower freeware sample size calculator, based on 2x2 Chi-squared test for wound healed status. Power calculation for sample size assumes 80% power and 5% two-sided confidence interval.

Table 4: standard care vs MedCu dressing. The hypothesis is that MedCu dressing performs better to a minimum 20% (effect size 0.41) in wound healed at week 12.

Since some patients may withdraw over the course of the 12-week trial period, a 20% dropout rate is calculated into each sample size. A 1:1 allocation to the two types of dressing is applied.

Note: There will be an option to expand sample size, subject to no safety concerns after initial sample size has been reached. This then allows wound healing comparison for purer sample of 'leg ulcers' and 'foot ulcers' separately from each other. For this purpose, the same effect size will be applied. The hypothesis is that MedCu dressing performs better to a minimum 20% (effect size 0.40), requiring a sample size 66 (taking into account same 30% drop-out/withdrawal rate)

Table 4, Sample size calculations

| | Sample size calculation | | | | | |
|------------------|---|---|--|--|--|--|
| | Standard care control dressing | Intervention dressing (MedCu copper dressing) | | | | |
| Ulcer healed | 40% | 60% | | | | |
| Ulcer not healed | 60% 40% | | | | | |
| | Power beta of 80%, Alpha p-value of 0.05, effect size 0.40 Sample size required without any drop-out: 50 patients Sample size with 30% attrition rate included: 66 patients Total of 66 patients, distributed as: - 33 Patients to receive MedCu dressing - 33 Patients to receive standard care dressing | | | | | |

The CONSORT guidelines require a statement on the number of patients assessed for eligibility (Schulz, Altman & Moher 2010). The number of patients screened but who did not meet the inclusion criteria or who declined to participate will be recorded, as will any patients who are lost to follow-up (Appendix 5).

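### Randomisation is called stratified by PUSH score but uses a non-restricted sequence, so as written it gives no balance on ulcer size and does not secure 33:33

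*Protocol*

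**What the plan says.** The protocol summary announces, under patient population, "Stratification for wound size at randomisation stage". Section 5.1.1 gives the detail: "The randomisation will be stratified by ulcer size, with one group being those with a PUSH score of up to and including 8", the other stratum being a score of 9 or more. The same section describes how the list is made: "A non-restricted randomised sequence will generated for each of the two groups using a freeware randomisation programme". Each allocation is then drawn from the trial's account with the named online service. No block size, minimisation scheme or other restriction appears anywhere in the protocol.

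On arm sizes, the summary states "Treatment will be random and 1:1 allocation: n = 33 standard of care and n = 33 MedCu copper dressing cases". Section 5.1 adds "A 1:1 allocation to the two types of dressing is applied", and Table 4 lists "33 Patients to receive MedCu dressing" with the same number for standard care.

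The primary analysis in section 7.2 is a chi-squared test of healed status at week 12, without adjustment for the stratification factor.

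**The concern.** Stratification balances a factor only if the sequence inside each stratum is restricted, by blocks or an equivalent device. Under a non-restricted sequence every allocation is independent of those before it. Splitting patients by PUSH score and then tossing independent coins within each part has the same distribution as ignoring PUSH score altogether. The protocol thus claims a property that its stated method does not have.

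Ulcer size is the only factor the protocol chose to balance, and section 7.3 lists it among the covariates for healing. With 66 patients or fewer in the analysis, a visible chance imbalance in size is quite possible, and the unadjusted primary test would not correct for it. Allocation cannot be repaired after enrolment, so the wording needs settling before recruitment starts.

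**Working it through.** **Inputs.** From the protocol: N = 66, 33 per arm, 1:1 (summary; section 5.1, Table 4); two PUSH strata cut at 8/9 and a non-restricted sequence (section 5.1.1); two-sided 5% level and 80% power (section 5.1). Not in the protocol, so assumed: 30% to 50% of patients in the smaller stratum (about 20:46 to 33:33); a difference in healing between strata of 20 to 40 points; blocks of 4 as an illustration.

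**The plan's own figure.** Table 4 states "Power beta of 80%, Alpha p-value of 0.05, effect size 0.40". A chi-squared test with 1 df, w = 0.40 and alpha 0.05 needs N = 50 (power 0.807). Then 50 × 1.3 = 65, taken up to an even 66. The 66 reproduces by that route. Whether w = 0.40 suits the tabulated healing rates is a separate matter and does not affect what follows.

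**Arm totals under simple allocation.** The number in one arm is X ~ Binomial(66, 0.5).
- P(X = 33) = 0.098.
- The 2.5% and 97.5% points are 25 and 41.
- P(arms differ by 10 or more, that is 38:28 or worse) = 0.268.
- P(41:25 or worse) = 0.064.

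**Does the stratification add balance?** Let D be the difference between arms in the share of patients from the smaller stratum. Simulation (200,000 trials per row for simple allocation):

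| Smaller stratum | Method | SD of D | P(\|D\| ≥ 20 points) |
|---|---|---|---|
| 30% | simple, strata ignored | 0.114 | 7.7% |
| 30% | simple, separate sequence per stratum | 0.114 | 7.6% |
| 50% | simple, strata ignored | 0.124 | 10.9% |
| 50% | simple, separate sequence per stratum | 0.124 | 10.8% |

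The two methods agree to within simulation error, as theory requires. With blocks of 4 inside each stratum, the SD of D falls to about 0.02, no 20-point gap arose in 20,000 trials, and arm totals never differed by more than 2. Exactly 33:33 still occurs only about 59% of the time.

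**Effect on the primary comparison.** Take no treatment effect, overall healing of 50%, equal strata and a healing difference d between strata. Approximately:
- simple allocation: SD = √(0.25 × 4/66) = 0.123 (0.124 by simulation, because arm sizes also vary);
- blocked within strata: SD = √((0.25 − 0.25d²) × 4/66), which is 0.121 at d = 0.20 and 0.113 at d = 0.40.

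Against 0.124 these are reductions of (0.124 − 0.121)/0.124, about 2.4% (close to 3% when both designs are simulated), and (0.124 − 0.113)/0.124, about 9%. Under simple allocation the mean estimated effect was zero and the type I error of the chi-squared test was about 5%. Under blocking with d = 0.40, the unadjusted chi-squared test had type I error of about 4%.

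**Power cost of unequal arms** (40% vs 60% healed, 66 analysed): 0.366 at 33:33, 0.362 at 37:29, 0.349 at 41:25.

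**The case against.** Simple randomisation is a valid design. Chance imbalance under it is part of the sampling error that the chi-squared test already allows for. A reader might infer that imbalance in ulcer size would confound or bias the primary result. The calculations do not support that: the estimate is unbiased and type I error stays near 5%. The power lost to unequal arms is also small. This part of the objection stands.

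A reader might also infer that the protocol promises a fixed 33:33 and breaks the promise. The numbers appear as planning figures, in section 5.1 under a heading about anticipated numbers. Simple allocation is 1:1 in expectation, and blocking in two strata does not guarantee 33:33 either. The supportable statement is that 33:33 is not secured.

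The word non-restricted may be loose drafting for a blocked list. How the account with the online service is set up cannot be seen from the protocol, so nothing should be claimed about it. If a blocked list is meant, the text still says the opposite and is the only specification of the method. The phrase about two groups might be read as the two arms, but the next sentence uses group for a PUSH stratum, and neither reading supplies a restriction.

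Finally, section 7.1 compares baseline characteristics, and section 7.3 plans a Cox model with baseline ulcer size as a covariate. An imbalance would therefore be seen and perhaps explored. That model is secondary and depends on sufficient data, so it neither restores the stratification nor changes the primary test.

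**Conclusion.** The inconsistency is real and should be fixed, but it does not invalidate the trial. As written, the stratification has no balancing effect, and arm totals can plausibly range from 25:41 to 41:25. The cost is chance imbalance in the one factor chosen for balance, which the primary test leaves uncorrected, with a modest loss of precision.

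The arm-size probabilities follow exactly from N = 66 and simple 1:1 allocation. The figure of 8% to 11% for a 20-point gap rests on the assumed stratum shares. The precision figure of about 3% to 9% rests on the assumed 20- to 40-point difference in healing between strata, with equal strata. The protocol gives neither the stratum shares nor the prognostic strength of PUSH score.

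**What to change.** In section 5.1.1, replace the non-restricted sequence with 1:1 allocation in randomly permuted blocks of varying, undisclosed size within each PUSH stratum (8 or below, 9 or above). In the summary and section 5.1, describe 33 per arm as a target.

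In section 7.2, make the primary comparison account for the PUSH stratum, for example with a Mantel-Haenszel or other stratum-adjusted test. Without this, the unadjusted chi-squared test becomes somewhat conservative under blocking if PUSH score is strongly prognostic, and part of the gain is lost.

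The cost is a few sentences and a matching set-up of the randomisation list before the first patient is randomised. The small downside is slightly more predictable allocation in an open-label trial, which varying and undisclosed block sizes limit.

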5.2 Eligibility criteria

5.2.1 Inclusion criteria

- Aged 18 years or over
- Women to be of non-childbearing potential (ie post-menopausal)
- Lower limb ulcer sized between 1 to 30 cm²
- Patients can be newly presenting to or existing users of the specialist service in question
- Patients with recurrent wounds, including multiple wounds, are eligible; largest eligible (ie <30cm²) ulcer to be index wound
- If infection occurs and systemic antibiotics applied, whilst in study, then this is not deemed an exclusion criterion.
- Chronicity: clinical diagnosis of ulcer with wound duration > 30 days and < 1 year from patient becoming aware.
- Prophylactic systemic antibiotic use is not an exclusion criterion
- Mental and physical ability to give consent and complete study activities
- Underlying pathology of lower limb ulcer can be venous, mixed venous-arteria, arterial, or through different underlying aetiology. Recognised co-morbidities that may contribute to the development of lower limb ulcers (e.g. diabetes, rheumatoid arthritis, peripheral vascular disease) are not an exclusion criterion.
- For leg ulcers: Patient is suitable for, and willing to wear, compression therapy, or valid clinical reason why they should not be prescribed compression therapy.

5.2.2 Exclusion criteria

- Under the age of 18 years
- Unable to fully understand the consent process and provide informed consent due to either language barriers or mental capacity

- Limited life expectancy, i.e. undergoing palliative care, or other condition that in opinion of researcher contraindicates participation
- Active infection in lower limb ulcer treated with systemic antibiotics within last 1 week (does not apply for prophylactic antibiotic regimes)
- Enrolled in other interventional research study related to patient's lower limb ulcer
- Previous participation in CUPRA study
- Awaiting significant surgical intervention related to vascular or skeletal system of the lower limbs, planned within three months (ie 12 week trial period)
- Known intolerance or allergy to materials used in MedCu copper dressing.

5.3 Early withdrawal of subjects

Patients have the right to withdraw from the trial at any time and without giving any reason. If a patient withdraws from the trial, any and all information gathered prior to the withdrawal will be included in the analysis, though no further data collection will occur. If a patient does not attend planned follow-up appointments then two more attempts will be made to contact the patient regarding the study. If still no contact can be made then the patient is deemed lost to follow-up and any collected study data will be retained. Appendix 2, INTERVENTION DEVIATION AND LEG ULCER INFECTION, covers study withdrawals in more detail.

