3. STUDY HYPOTHESIS

3.1 Primary objective

To determine the efficacy of MedCu copper oxide impregnated wound dressing for the management of lower limb ulcers, measured through wound status (healed vs non-healed) at 12 weeks post-baseline

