APPENDIX 1. INTERVENTION DEVIATION AND LOWER LIMB ULCER INFECTION

There may be incidences where a participant may either:

- Develop a reaction to the allocated dressing.
- Becomes completely non-compliant (possibly due to allocated dressing being uncomfortable, or eg hospital admission)
- Improve to such an extent that allocated dressing is no longer indicated.

In such instances the patient and/or clinician can opt to stop or pause treatment with the dressing in question. If this occurs, this needs to be recorded (date and reason), and the decision can then be made to either:

- Discontinuation of intended dressing due to improvement in symptoms (including wound healed). Participant will still continue to be assessed as per planned dates and timepoints.
- Change over to an alternative dressing that is not the originally allocated type. This is allowed but only if there are clinical indications to do so or at patient request if they cannot tolerate the allocated dressing. Patient can later in trial period be transferred back to original allocated bandage type if required.
- Pausing or discontinuation of wound dressing when not clinically indicated. Even if lower limb ulcer persists and patient no longer wears allocated dressing, they can still continue in the trial if they wish. Outcome measures will continue to be recorded as per planned dates and time points.
- Pause or discontinuation due to adverse event. Patient can remain in trial provided they are capable to continue with follow-up schedule and completion of outcome measures. If not possible, see next point regarding 'Withdraw patient from study'.
- Withdraw patient from study.
 - o At the request of the patient
 - For clinical reasons, eg if the leg ulcer has deteriorated to such an extent that emergency surgical or medical intervention is required which means return to use of any dressing in reasonable time frame (within time to next trial follow-up visit) is not feasible. In this case, this needs to be reported as a (Serious) Adverse Event if discontinuation is due to deterioration of the index wound or index leg only.

When overall trial participation for a patient is finished early, the participant will still be asked to complete the relevant questionnaires (provided they have capacity to do so):

- Week 4, week 8 and week 12 VEINES Sym questionnaire
- Week 12 EQ5D5L QoL questionnaire

Infection and use of antibiotics during trial

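### For patients whose trial participation ends early, section 5.3 and Appendix 1 contradict each other on further data collection, and neither collects week-12 healed status, the primary outcome

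*Protocol*

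**What the plan says.** The primary objective (3.1) is "measured through wound status (healed vs non-healed) at 12 weeks post-baseline". Section 4.5.1 defines healing and requires no minimum duration. Table 3 in 4.3 schedules wound status at weeks 4, 8 and 12, the same follow-up weeks as VEINES-Sym.

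On patients who withdraw, section 5.3 states that "any and all information gathered prior to the withdrawal will be included in the analysis, though no further data collection will occur". It refers the reader to Appendix 2 for detail. Appendix 2 is the wound formulary, and the withdrawal text is in Appendix 1.

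Appendix 1 distinguishes two groups:
- **Dressing stopped or paused, patient stays in the trial.** "Outcome measures will continue to be recorded as per planned dates and time points". Wound status is therefore still collected.
- **Patient withdrawn from the study.** The routes are the patient's own request and clinical reasons, the latter illustrated by "eg if the leg ulcer has deteriorated to such an extent that emergency surgical or medical intervention is required".

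The appendix then adds: "When overall trial participation for a patient is finished early, the participant will still be asked to complete the relevant questionnaires". Its list has two items: "Week 4, week 8 and week 12 VEINES Sym questionnaire" and "Week 12 EQ5D5L QoL questionnaire". Wound status, ulcer size and PUSH score are not on it.

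Section 7.2 plans a chi-squared test on a per-protocol basis, using only participants with data.

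**The concern.** A site with a patient who leaves the trial at week 5 has two instructions: collect nothing more (5.3), or collect questionnaires up to week 12 (Appendix 1). Different sites or staff may choose differently.

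Under the fuller rule, the trial still contacts the patient at week 12 but asks only for secondary questionnaires. The data kept from before withdrawal do not fill the gap, because the endpoint is status at week 12. Even an ulcer recorded as healed at week 4 or 8 can have recurred by then, and 7.1 plans to record this.

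The primary comparison is at stake. A patient withdrawn because the ulcer deteriorated is more likely to be unhealed at week 12 than a patient who completes. With no week-12 status, that patient drops out of the 7.2 analysis. Participants are not blinded (5.1.1), so withdrawal may also differ by arm. An analysis plan cannot restore an outcome that was never collected.

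**Working it through.** **1. The two rules side by side, for patients whose participation ends early**

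| Item | 5.3 | Appendix 1 |
|---|---|---|
| VEINES-Sym, weeks 4, 8, 12 | not collected | requested |
| EQ-5D-5L, week 12 | not collected | requested |
| Healed status, week 12 | not collected | not listed |

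The first two rows conflict. The third is a gap under both rules.

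**2. The plan's own attrition figures (5.1 and Table 4)**

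Inputs: effect size w = 0.40, alpha 0.05, power 80%, 50 patients before dropout, 66 with 30% attrition, 33 per arm. The text of 5.1 also states 20% dropout.

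- With a noncentral chi-square on 1 degree of freedom and w = 0.40 taken as given, the smallest total with at least 80% power is 50 (power 80.7%). This reproduces the plan.
- 50 × 1.30 = 65, rounded up to an even 66. This also reproduces the plan.

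The documents therefore support three sizes of loss:
- 50 completers of 66: 16 missing, 8 per arm.
- 30% of 66 = 19.8: about 20 missing, 10 per arm.
- 20% of 66 = 13.2: about 13 missing, up to 7 per arm.

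**3. How far an arm's healing rate is left open**

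Assumptions: all planned attrition is early finish without a week-12 status, and 40% of those observed are healed (the control rate in Table 4). With m missing of 33 and h healed among those observed, the lower bound is h/33 (no missing patient healed), the upper bound is (h + m)/33 (all healed), and the width is m/33.

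| m | Observed | h at 40% | Lower | Upper | Width |
|---|---|---|---|---|---|
| 7 | 26 | 10.4 | 10.4/33 = 31.5% | 17.4/33 = 52.7% | 21.2 points |
| 8 | 25 | 10 | 10/33 = 30.3% | 18/33 = 54.5% | 24.2 points |
| 10 | 23 | 9.2 | 9.2/33 = 27.9% | 19.2/33 = 58.2% | 30.3 points |

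The values 10.4 and 9.2 are expected numbers, not possible counts. With 9 healed of 23, the last row runs from 9/33 = 27.3% to 19/33 = 57.6%. Each status recovered, and used in the analysis, narrows the range by 1/33 = 3.0 points.

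**4. The same bounds on the difference between arms**

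- 8 missing per arm, 10/25 against 15/25 healed: observed difference 5/25 = 20 points. Extremes: (15 − 18)/33 = −9 points and (23 − 10)/33 = +39 points.
- 10 missing per arm, 9/23 against 14/23 healed: observed difference 5/23 = 22 points. Extremes: (14 − 19)/33 = −15 points and (24 − 9)/33 = +45 points.

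**The case against.** **Scope.** A reader might infer that the outcome is lost whenever a patient leaves the allocated dressing. The documents do not support that. Appendix 1 keeps scheduled outcome recording for patients who stop or pause the dressing and lets those who change it stay in the trial. Patients with adverse events can also stay if able to follow the schedule. Only those withdrawn from the study lose the outcome.

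**Two rules for two groups.** Section 5.3 could be read as covering withdrawal by the patient and Appendix 1 as covering other early finish. This fails, because Appendix 1 lists withdrawal at the patient's request and makes no exception for it. Alternatively, Appendix 1 could govern as the more detailed text. That would settle the conflict but still leave healed status uncollected.

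**Reasons for loss.** A reader might infer that the missing outcomes are mainly informative. The protocol gives no split by reason. Deterioration is one example under one of two withdrawal routes, and loss to follow-up is a further source. The text supports only a loss that is partly outcome-related.

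**Size.** Ten missing per arm is not the only figure the plan implies, since 50 of 66 completers means 8 and 20% dropout means about 7. Some of the loss will be patients who cannot be contacted (5.3), whose status may not be recoverable. The upper bounds also assume that every missing patient healed, which is implausible for those withdrawn for deterioration. This objection stands, so the ranges are upper illustrations.

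**Obtainability.** Routine records may not show what 4.5.1 requires, especially after emergency surgery, and the consent form is not in the document reviewed. This also stands. Recovery is plausible for patients still in wound care, but not assured.

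**Conclusion.** The point holds for patients whose trial participation ends early. Section 5.3 and Appendix 1 contradict each other, and neither obtains the primary outcome at week 12. Because a named withdrawal route is deterioration of the ulcer, the missing outcomes are partly related to the endpoint, and the available-data comparison in 7.2 can be biased.

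If all planned attrition is early finish and 40% of those observed are healed, an arm's rate is left open from 30% to 55% with 8 missing and from 28% to 58% with 10 missing. Under the step 4 assumptions, the extremes for the difference between arms include a reversal of sign. These figures show what the missing data could hide. They do not predict bias of that size, and its direction cannot be derived from the protocol.

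This should be corrected. It concerns what is collected and what patients consent to, which belongs in the protocol and cannot be left to an analysis plan.

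**What to change.** 1. **Reconcile 5.3 with Appendix 1.** Separate leaving study visits (collection continues, with consent) from withdrawing consent to data collection (collection stops). Use the same terms in both places.
2. **Correct the appendix reference in 5.3** from Appendix 2 to Appendix 1.
3. **Add week-12 index-ulcer healed status to the early-finish list in Appendix 1.** Take it at the week-12 contact already planned for the questionnaires, or from the routine care record where that record allows the 4.5.1 definition to be judged. Record which source was used.
4. **State in 7.2 that these recovered outcomes enter the primary comparison in the allocated arm.** Otherwise the per-protocol wording could exclude them again and the collection would gain nothing.
5. **Optional sensitivity analysis:** count patients withdrawn for deterioration, with no recovered status, as not healed. This is an imputation and does not replace collecting the outcome.

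The cost is a small amendment to the protocol and, where needed, to the consent form, passed through the review bodies named in 9.1. Some statuses would come from care records and not from a study visit, so they may be less uniform. Patients who cannot be contacted, or who refuse further collection, would still be missing.
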